6. Patients who received  $\leq 14$  days of tamoxifen or a NSAI (letrozole or anastrozole) with or without goserelin or goserelin  $\leq 28$  days for advanced breast cancer prior to randomization are eligible. Patients must continue treatment with the same hormonal agent + goserelin during the study. No treatment interruption is required for these patients prior to randomization.

**Note:** Patients who are receiving goserelin for reasons other than for advanced breast cancer treatment are eligible (e.g endometriosis). Patients who received  $\leq 28$  days goserelin for advanced breast cancer are eligible.
7. Patients who have received up to 1 line of chemotherapy for advanced breast cancer and have been discontinued 28 days before randomization are eligible.

**Note:** If a cytotoxic chemotherapy regimen was discontinued for reasons other than disease progression and lasted less than 21 days, this regimen does not count as a prior line of chemotherapy.
8. Patient has a histologically and/or cytologically confirmed diagnosis of estrogen-receptor positive and/or progesterone receptor positive breast cancer by local laboratory (based on most recently analyzed biopsy).
9. Patient has HER2-negative breast cancer (based on most recently analyzed biopsy) defined as a negative in situ hybridization test or an IHC status of 0, 1+ or 2+. If IHC is 2+, a negative in situ hybridization (FISH, CISH, or SISH) test is required by local laboratory testing.
10. Patient must have either:
  - Measurable disease, i.e., at least one measurable lesion as per RECIST 1.1 criteria.

**OR**

  - If no measurable disease is present, then at least one *predominantly* lytic bone lesion must be present (patients with no measurable disease and only one *predominantly* lytic bone lesion that has been previously irradiated are eligible if there is documented evidence of disease progression of the bone lesion after irradiation).
11. Patient has ECOG PS 0 or 1.
12. Patient has adequate bone marrow and organ function as defined by the following laboratory values (as assessed by central laboratory):

- Absolute neutrophil count  $\geq 1.5 \times 10^9/L$ .
  - Platelets  $\geq 100 \times 10^9/L$ .
  - Hemoglobin  $\geq 9.0$  g/dL.
  - Potassium, sodium, calcium (corrected for serum albumin), and magnesium within normal limits of the central laboratory or corrected to within normal limits with supplements before the first dose of study medication
  - INR  $\leq 1.5$ .

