11. Patient has any other concurrent severe and/or uncontrolled medical condition that would, in the investigator's judgment, contraindicate patient participation in the clinical study (e.g., chronic pancreatitis, chronic active hepatitis, etc.).
12. Clinically significant, uncontrolled heart disease and/or cardiac repolarization abnormality, including any of the following:
  - History of angina pectoris, symptomatic pericarditis, myocardial infarction, or coronary artery bypass graft (CABG) within 6 months prior to study entry
  - Documented cardiomyopathy
  - Left Ventricular Ejection Fraction (LVEF)  $< 50\%$  as determined by Multiple Gated acquisition (MUGA) scan or echocardiogram (ECHO)
  - Clinically significant cardiac arrhythmias (e.g., ventricular tachycardia), complete left bundle branch block, high-grade AV block (e.g., bifascicular block, Mobitz type II and third degree AV block)
  - Long QT syndrome or family history of idiopathic sudden death or congenital long QT syndrome, or any of the following:
    - Risk factors for Torsades de Pointe (TdP) including uncorrected hypokalemia or hypomagnesemia, history of cardiac failure, or history of clinically significant/symptomatic bradycardia
      - resting heart rate  $< 50$  at rest, by the triplicate ECG
      - resting heart rate  $> 90$  at rest, by the triplicate ECG
      - Systolic blood pressure  $> 160$  or  $< 90$  mmHg
      - On screening, inability to determine the QTcF interval on the ECG (ie: unreadable or not interpretable) or QTcF  $> 450$  msec (using Fridericia's correction). All as determined by the average of the triplicate screening ECG, per central review.

13. Patient is currently receiving any of the following substances and cannot be discontinued 7 days prior to the start of the treatment:
  - Known strong inducers or inhibitors of CYP3A4/5, including grapefruit, grapefruit hybrids, pomelos, star-fruit, and Seville oranges.
  - Medications with a known risk to prolong the QT interval or induce Torsades de Pointes that cannot be discontinued or replaced by safe alternative medication (e.g. within 5 half-lives or 7 days prior to starting study drug).
  - Medications that have a narrow therapeutic window and are predominantly metabolized through CYP3A4/5.
  - Additionally, for patients receiving tamoxifen: known strong inducers or inhibitors of CYP2D6.
  - Herbal preparations/medications and dietary supplements (except for vitamins).

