### 6.3.1.6 Additional follow-up for QTc prolongation

**Table 6-5 LEE011/placebo dose adjustment and management recommendations for QTcF prolongation (CTC AE v4.03)**

Grade	Dose Modification
For All Grades	
 
1. Check the quality of the ECG and the QT value and repeat if needed
 
2. Perform analysis of serum electrolytes (K+, Ca++, Phos, Mg++). If outside the normal range, interrupt LEE011/placebo administration, correct with supplements or appropriate therapy as soon as possible, and repeat electrolytes until documented as normal.
 
3. Review concomitant medication usage for the potential to inhibit CYP3A4 and/or to prolong the QT interval.
 
4. Check compliance with correct dose and administration of LEE011/placebo.
 

Grade 1* QTc 450-480 ms	Perform steps 1-4 as directed in “For All Grades”. No dose adjustment required.
Grade 2* QTc 481-500 ms	
Interrupt LEE011/placebo. Perform steps 1-4 as directed in “For All Grades.”
 
Perform a repeat ECG within one hour of the first QTcF of ≥ 481 ms. Repeat ECG as clinically indicated until the QTcF returns to < 481ms, restart LEE011/placebo with dose reduced by 1 dose level. Refer to Table 6-2 for dosing schedule.
 
If QTcF ≥ 481 ms recurs, ribociclib should be reduced again by 1 dose level.
 
 
• Repeat ECGs 7 days and 14 days after dose resumption (then as clinically indicated) for any patients who had therapy interrupted due to QTcF ≥ 481 ms
 

Grade	Dose Modification

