### 6.3.1.8 Guidance for all other adverse reactions

Consider performing an analysis of serum potassium, calcium, phosphorus, and magnesium for all adverse reactions, if indicated. If electrolyte values are outside of the normal range, interrupt LEE011/placebo administration, correct electrolytes with supplements or appropriate therapy as soon as possible, and repeat electrolyte testing until documented normalization of the electrolytes.

For all other adverse events, including Toxic Epidermal Necrolysis (TEN), which is a grade 4 event by CTCAE, please follow recommendations in [Table 6-7](#).

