At the time of protocol amendment 6, minimal follow up for all patients on study treatment is 36 months. Central laboratory hematology, biochemistry and ECG assessments will cease and all tests should be performed locally. Patients originally randomized to the LEE011 arm and continuing with open label LEE011 plus endocrine treatment and patients in the placebo arm that elect to continue with their current treatment (i.e. endocrine treatment alone), should have safety assessments and clinic visits as frequently as clinically indicated, but not less frequently than every 12 weeks. Tumor assessments will continue as clinically indicated as described in Section 7.2.1.1 (see Table 7-1a). Instructions for patients electing to cross-over from placebo to LEE011 at the next scheduled visit:

[figure not shown]
Patients currently receiving placebo plus NSAID plus goserelin and electing to cross-over to LEE011 plus NSAID plus goserelin, can commence LEE011 on Day 1 of their next planned cycle.

Of Note: Patients currently receiving placebo plus tamoxifen plus goserelin and elect to cross-over to the LEE011 arm, must first switch from tamoxifen to an NSAID. At least 5 tamoxifen half-lives (35 days) must elapse, before LEE011 is added. See [Section 6.1](#) for more details.

All patients commencing LEE011 after cross-over from placebo will need to have local hematology, electrolyte and liver function biochemistry tests every two weeks for the first 2 cross over cycles of LEE011 treatment, then at the beginning of cross over cycles 3 to 6, then as clinically indicated, but not less frequently than every 12 weeks. They need to have ECG for QT assessment on the first day before the administration of LEE011. LEE011 should be initiated only in patients with QTcF values <450 msec. The ECGs should be repeated on cross over Cycle 1 Day 15, on cross over Cycle 2 Day 1 and then as clinically indicated. The assessment schedule for patients who will cross-over is presented in [Table 7-1b](#). Consult [Table 6-3](#), [Table 6-4](#) and [Table 6-5](#) for monitoring frequency in cases of hematologic toxicity, liver function abnormalities or QT prolongation respectively.

**Table 7-1a Visit evaluation schedule – Patients that, after protocol amendment 6, continue with their originally randomized study treatment**

Visit name	Category	Reference to Protocol Section	Screening Phase		Treatment Phase							Post-treatment Phase			

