			Cycle 1	Cycle 2	Cycle 3	Subsequent cycles	End of study treatment (EOT) within 15 days from the last dose	Safety follow up EOT + 30 days	Efficacy Follow up	Survival Follow up (Every 12 weeks)				
Treatment days			-28 to -1	-14 to -1	1	15	1	1	15	16	1			N/A
Liver biopsy for hepatic toxicity	D	7.2.4.2			As clinically indicated in case of liver toxicity									
Patient Reported Outcome														
EORTC QLQ-C30	D	7.2.6	x											
EORTC QLQ-BR23	D	7.2.6	x											
EQ-5D-5L	D	7.2.6	x											
Treatment														
Tamoxifen or NSAI	D	6			Daily									
Goserelin	D	6			Days 1 of each cycle									

**Table 7-1b Visit evaluation schedule – Cross over treatment cycles for patients who cross over from placebo to LEE011 after protocol amendment 6**

	Category	Reference to Protocol Section	Treatment Phase (only applies to cross-over patients for cross over treatment cycles – after that refer to Table 7-1a for schedule for EOT and post treatment phase assessments)						
Visit name			Cross over Cycle 1		Cross over Cycle 2		Cross over Cycles 3-6		All subsequent Cross over cycles
Treatment days			1	15	1	15	1	1	
Physical Examination									
Physical examination	S	7.2.2.1	x		x		x	Every 3 rd cycle	
Performance status (ECOG)	D	7.2.2.4	x		x		x	Every 3 rd cycle	
Weight	D	7.2.2.3	X		x		x	As clinically indicated	
Vital signs	D	7.2.2.2	x		x		x	Every 3 rd cycle	
Laboratory assessments									
Hematology	D	7.2.2.5.1	x	x	x	x	x	Every 3 rd cycle	
Biochemistry (including fasting glucose)	D	7.2.2.5.2	x	x	x	x	x	Every 3 rd cycle	
Coagulation	D	7.2.2.5.3	As clinically indicated						
Tumor Assessments									
Tumor Assessment	D	7.2.1.1	As clinically indicated						
Fluid/Tissue collection results (if available)	D	7.2.1	As clinically indicated						

	Category	Reference to Protocol Section	Treatment Phase (only applies to cross-over patients for cross over treatment cycles – after that refer to Table 7-1a for schedule for EOT and post treatment phase assessments)						
Visit name			Cross over Cycle 1		Cross over Cycle 2		Cross over Cycles 3-6		All subsequent Cross over cycles
Treatment days			1	15	1	15	1	1	
Whole body bone scan	D	7.2.1	As clinically indicated						
Safety									

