**Table 7-4 Local clinical laboratory parameters collection plan**

Test Category	Test Name
Hematology	Complete blood count (CBC) including total white blood cell count (WBC) with differential (neutrophil count including lymphocyte, monocyte, eosinophil, and basophil counts) RBC, hemoglobin (Hgb), hematocrit (Hct), and platelet count.
Biochemistry (with fasting glucose)	Total proteins, albumin, total bilirubin, direct bilirubin, indirect bilirubin, AST, ALT, GGT, bicarbonate, calcium, corrected calcium, chloride, creatinine kinase, alkaline phosphatase, amylase, lipase, magnesium, sodium, potassium, urea or BUN, uric acid, serum creatinine, and fasting glucose
Fasting Lipid Panel	Total cholesterol, LDL-cholesterol, HDL-cholesterol and triglycerides (fasting)
Urinalysis	Macroscopic Panel (Dipstick) (Color, Bilirubin, Blood, Glucose, Ketones, Leukocytes esterase, Nitrite, pH, Protein, Specific Gravity, Urobilinogen) If there are any significant findings on the dipstick then a microscopic evaluation should be measured: Microscopic Panel (WBC and RBC sediments, Casts, Crystals, Bacteria, Epithelial cells)
Coagulation	INR
Other Test	FSH, [REDACTED]

Test Category	Test Name
[REDACTED]	

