**Table 7-5 Central ECG collection plan**

Cycle	Patients	Day	Time	ECG Type
Screening	All	-14 to -1	Anytime	Triplicate 12 Lead
1	All	Day 1	Pre-dose 	Triplicate 12 Lead
	All	Day 15 	Pre-dose 	Triplicate 12 Lead
	All		2 h post-dose (± 15 min)	Triplicate 12 Lead
	All		4 h post-dose (± 15 min)	Triplicate 12 Lead
2	All	Day 1	Pre-dose 	Triplicate 12 Lead
3	All	Day 1	Pre-dose 	Triplicate 12 Lead

Cycle	Patients	Day	Time	ECG Type
3	All	Day 15 	Pre-dose 	Triplicate 12 Lead
	All		2 h post-dose (± 15 min)	Triplicate 12 Lead
4	All	Day 1	Pre-dose 	Triplicate 12 Lead
5	All	Day 1	Pre-dose 	Triplicate 12 Lead
6	All	Day 1	Pre-dose 	Triplicate 12 Lead
			2h post-dose (± 15 min)	Triplicate 12 Lead
All other cycles	As clinically indicated		Anytime	Triplicate 12 Lead
EOT			Anytime	Triplicate 12 Lead
Unscheduled ECG			Anytime	Triplicate 12 Lead
 The exact date and time of dosing must be recorded on the appropriate eCRF.  ECG assessments are to be done prior [REDACTED] (if applicable)				

ECG Schedule of assessments for cross over patients:

Patients	Cross Over Cycle	Day / time	ECG type
All	1	1/Pre-dose	Triplicate 12 Lead
All	1	15/anytime	Triplicate 12 Lead
All	2	1/ anytime	Triplicate 12 Lead
All	All other cycles as clinically indicated		Triplicate 12 Lead

In order for an accurate evaluation of baseline QTcF, a total of three 12-lead ECGs will be performed pre-dose on Cycle 1 Day 1.

**Note:** In order to ensure ECG evaluation is received from the central laboratory for eligibility assessment, it is advisable to perform the ECG at least 24 hours prior the scheduled randomization date.

If any of the triplicate readings include an abnormal ECG or an average QTcF value of  $\geq 481$  is obtained at any time after randomization, study treatment must be interrupted, repeat ECG (triplicate) and follow management guidelines detailed in [Table 6-5](#).

An unscheduled ECG may be repeated at the discretion of the investigator at any time during the study and as clinically indicated. Unscheduled ECGs with clinically significant findings should be collected in triplicate. Local cardiologist ECG assessment may be performed at any time during the study at the discretion of the investigator.

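### The first crossover dose of LEE011 depends on a pre-dose QTcF but not on a reviewed electrolyte result, so the dose or doses before the local result is read are uncovered

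*Protocol*

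**What the plan says.** **At crossover.** Section 7.1 asks for an ECG on the first day before LEE011 is given, and adds: "LEE011 should be initiated only in patients with QTcF values <450 msec". The same paragraph asks for local hematology, electrolyte and liver tests every two weeks in the first two crossover cycles. For these it gives neither an order relative to the dose nor a limit. Table 7-1b, which covers "Cross over treatment cycles for patients who cross over from placebo to LEE011 after protocol amendment 6", marks biochemistry on crossover Cycle 1 Day 1. The local panel in Table 7-4 includes "calcium, corrected calcium, chloride, creatinine kinase, alkaline phosphatase, amylase, lipase, magnesium, sodium, potassium". Patients on tamoxifen must also switch to an NSAI and wait 35 days before starting LEE011 (Section 6.1).

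**At original entry.** Inclusion criterion 12 (Section 5.2) required potassium, sodium, corrected calcium and magnesium to be within central laboratory limits, "or corrected to within normal limits with supplements before the first dose of study medication". Exclusion criterion 12 (Section 5.3) listed "Risk factors for Torsades de Pointe (TdP) including uncorrected hypokalemia or hypomagnesemia" as well as a screening QTcF above 450 msec.

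**On treatment.** Section 7.2.2.7.1 has a rule beginning "If any of the triplicate readings include an abnormal ECG or an average QTcF value of" 481 msec or more; it interrupts treatment and sends the patient to Table 6-5. Step 2 of that table reads: "Perform analysis of serum electrolytes (K+, Ca++, Phos, Mg++). If outside the normal range, interrupt LEE011/placebo administration". Section 6.3.1.8, on other adverse reactions, says: "If electrolyte values are outside of the normal range, interrupt LEE011/placebo administration, correct electrolytes with supplements or appropriate therapy as soon as possible".

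**The concern.** The protocol recognizes two separate QT-related hazards: a long QTcF and uncorrected low potassium or magnesium. At entry each had its own condition. The crossover instructions carry over the QTcF condition and omit the electrolyte one. With enrollment closed since 01-Aug-2016, crossover is the only way a study patient newly starts LEE011.

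The pre-dose ECG does not stand in for the laboratory result, because it is recorded before any LEE011 exposure. Section 1.2.1.3 reports that QT changes become evident by Day 8 and later. At stake is a correctable risk factor for torsades in patients starting a QT-prolonging drug.

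**Working it through.** The plan states no figure to reproduce here. The check is a comparison of texts plus a count of the patients concerned.

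**1. Compare the two Day 1 tests at crossover (Section 7.1, Table 7-1b).**

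| Test | Scheduled Day 1 | Must precede the dose | Limit for starting |
|---|---|---|---|
| ECG | yes | yes | QTcF below 450 msec |
| Biochemistry | yes | not stated | none stated |

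**2. Ask whether another rule supplies the missing condition.**

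- *Inclusion 12 and exclusion 12.* These apply at enrollment. Inclusion 12 is tied to the first dose of study medication, which for these patients was years earlier: Section 7.1 puts minimum follow-up at 36 months at Amendment 6. Neither Section 7.1 nor Table 7-1b reapplies them.
- *Table 6-5.* Its lowest grade begins at QTc 450 ms, whereas the starting condition is QTcF below 450 msec. A patient cleared to start can reach the electrolyte step only through an otherwise abnormal ECG (Section 7.2.2.7.1).
- *Section 6.3.1.8.* It opens with an optional check for adverse reactions, then directs interruption and correction of out-of-range values. It acts on a known result.
- *Section 7.2.2.5.* The investigator must review all laboratory reports, with no timing relative to the dose.
- *Section 6.1.1.2.* Visit-day dosing is supervised in the clinic and the ECG comes before the dose. The text does not mention waiting for the laboratory.
- *Earlier results.* For patients staying on their original treatment, Table 7-1a schedules biochemistry every third cycle: 3 × 28 = 84 days, or 12 weeks. The last value before crossover may be that old.

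None of these makes the Day 1 electrolyte result a condition for the first crossover dose.

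**3. Ask what happens once an abnormal result is read.** Under Sections 8.1.1 and 8.1.2.1, a laboratory abnormality that needs therapy or a change in study medication is an adverse event. Section 6.3.1.8 then calls for interruption, correction and repeat testing until normal. Table 6-7 requires interruption at Grades 2 and 3 and discontinuation at Grade 4. The uncovered interval runs from the first dose to review of the result.

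**4. Count the patients.** Amendment 7 gives 35 placebo-arm patients on treatment on 08-Jan-2020, of whom 8 had crossed over: 35 − 8 = 27. This is a ceiling. From Amendment 6 (18-Jul-2019) to 08-Jan-2020 is 174 days; 174 / 7 = 24.9 weeks, and 24.9 / 12 = 2.1 of the longest permitted visit intervals. Some of the 27 may already have declined. Site approval dates and numbers declining are not given.

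**The case against.** The strongest reply is that the protocol already deals with abnormal electrolytes. Crossover patients are on study treatment, their laboratory reports must be reviewed, and a low potassium or magnesium needing correction falls under Section 6.3.1.8 and Table 6-7. Crossover also rests on the investigator's individual benefit-risk decision (Amendment 6). These patients met the electrolyte criterion at entry, and testing continues every two weeks for two cycles. Most of this stands. It rules out reading the protocol as allowing a patient with known uncorrected hypokalemia to be started and kept on LEE011, or as never requiring laboratory review. It does not supply a review before the first dose.

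A reader might also infer up to 14 doses on uncorrected electrolytes (Days 1 to 14, before the Day 15 draw). The documents do not support that as a consequence of the text. It assumes the Day 1 result is ignored despite Sections 7.2.2.5 and 6.3.1.8, and with the general ±3 day window a Day 18 draw would give 17. Either figure describes a site failing to act.

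Section 1.4.1.1 reports a treatment-related sudden death on ribociclib plus letrozole in a patient with grade 3 hypokalemia and QTcF 483 msec. It shows the two hazards together on this drug. It is not evidence about starting with QTcF below 450 msec: 483 msec falls in Grade 2 of Table 6-5, and potassium at first dose is not reported.

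Finally, Figure 6-1, a figure within the Section 7.1 crossover text and the IRT settings cannot be seen. The claim of absence covers the readable text only.

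**Conclusion.** The point holds in a narrow form. Following the readable text exactly, a patient with low potassium or magnesium, an otherwise normal ECG and QTcF below 450 msec can take a first dose of LEE011 before the Day 1 result is read. The exposure is one dose if the result is read and acted on that day, and longer only by the local turnaround and review time, which the documents do not give. At most 27 patients were concerned on 08-Jan-2020, probably fewer. The documents give no rate of electrolyte abnormality in this group, so no number of affected patients can be stated.

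No efficacy or safety conclusion of the trial changes: PFS and OS had already met their criteria, and later analyses are descriptive. This is a cheap safety improvement. It assumes that the figures and the IRT contain no pre-dose electrolyte check.

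**What to change.** Add to the Section 7.1 crossover instructions, and as a note to the biochemistry row of Table 7-1b: LEE011 may be started only when potassium, magnesium and corrected calcium are within local laboratory normal limits, or have been corrected to within them, on a recent local result reviewed before the first crossover dose. To define recent, the seven-day allowance that Section 7.1 already uses for Cycle 1 Day 1 laboratory tests would serve.

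Sodium is left out deliberately. It was in inclusion criterion 12, but it is neither a named torsades risk factor in exclusion criterion 12 nor in step 2 of Table 6-5, and an isolated sodium deviation should not hold up treatment.

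The cost is one sentence and one table note. The test is already scheduled, so no routine sample is added; a correction would need a repeat test. The first dose may be delayed briefly while the local result is awaited or a value is corrected.

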### 1.2.1.3 Clinical safety of LEE011

As of 15-Jun-2015, 157 patients have been treated with single agent LEE011 in the first-in-human (FIH) phase I study; 85 patients have been treated in the initial dose escalation part for the 3 week on/1 week off regimen and 47 patients in the dose expansion part of the study; 18 patients were enrolled for the continuous dosing regimen with LEE011 and, 7 patients were enrolled in the liquid formulation cohort.

Patients with advanced solid tumors or lymphomas were treated with increasing doses of LEE011 orally, once daily (qd) for 21 days followed by a 1-week rest (28-day cycle). Doses ranging from 50 mg to 1200 mg were evaluated on this schedule. Treatment has been discontinued in 120 (90%) patients; the primary reasons for treatment discontinuation were: disease progression (106 [80%] patients); AEs (7 [5%] patients); death (2 [1.5%] patients); withdrawal of consent (3 [2%] patient); and loss to follow up (1 [1%] patient).

The most frequently reported AEs ( $\geq 10\%$ ), regardless of grade, causality and LEE011 dose were: nausea (52.3%); fatigue (40.9%); diarrhea (37.1%); vomiting (35.6%); neutropenia (34.1%); anemia (32.6%); decreased appetite (23.5%), thrombocytopenia (23.5%); white blood cell count decrease (22.7%); leukopenia (22%); constipation (21.2%); dyspnea (20.5%); asthenia (19.7%); cough (18.2%); hyperglycemia (17.4%); headache, hypoalbuminemia (16.7% each); ECG QT prolonged (15.9%); abdominal pain, back pain, lymphocyte count decrease, pyrexia (15.2% each); AST increase, blood creatinine increased, dizziness, lymphopenia (14.4% each), peripheral edema (13.6%), neutrophil count decreased (12.9%); ALT increase; pain in extremity (12.1% each) and hypocalcemia (11.4%).

For either continuous or intermittent dosing, the onset of neutropenia (most frequently Grade 2) typically occurs by Day 15, reaching a nadir in the third or fourth week with recovery during the week of drug holiday for the three weeks on/one week off schedule. Some patients require additional time for recovery (7 to 14 days). QT changes become evident in the first cycle by Day 8 and later (once steady state is reached), are associated with the maximum drug levels between 1 to 8 h post-dose, and remain stable or improve in subsequent cycles.

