#### 1.2.1.5 Clinical pharmacokinetics of LEE011

The pharmacokinetics of LEE011 have been evaluated following single and repeat daily doses in the ongoing single agent, phase I study in patients with advanced solid tumors or lymphomas [CLEE011X2101]. Following oral administration of LEE011, peak plasma concentrations (Cmax) are achieved at approximately 1-4 hours post-dose. LEE011 plasma exposure (Cmax and AUC0-24h) demonstrates slightly over-proportional increases across the dose range tested (50 to 1200 mg). Steady-state is generally reached by Day 8 and the mean effective T1/2 based on accumulation ratio (i.e., T1/2, acc) ranged from 12.3 to 42.9 hours across the dose range tested.

The mean accumulation ratio (Racc) calculated from AUC0-24h at steady-state and AUC0-24h after a single dose across the studied doses ranged from 1.35 to 3.11. At the recommended dose for future development (600 mg), steady-state plasma Cmax (n=56) ranges from 606-6170 ng/mL (geometric mean = 1790 ng/mL or 4.1  $\mu$ M), median Tmax (n=72) is 2.1 h, and AUC0-24h (n=53) ranges from 6770-90600 ng\*h/mL (geometric mean = 23600 h\*ng/mL). At this dose, inter-patient variability in Cmax and AUC is 62% and 66%, respectively, as assessed by geometric mean percent coefficient of variation (% CV). At the 600 mg dose level, LEQ803, an active metabolite of ribociclib, accounted for approximately 8% (geometric mean) of ribociclib AUC0-24h after single and multiple doses.

In the human ADME study [CLEE011A2102], a single oral dose of 600 mg [C]LEE011 was administered to 6 healthy male subjects. The majority of the administered dose was excreted in feces (69.1%), with a minor amount excreted in urine (22.6%). Absorption was estimated to be approximately 58.8%. Ribociclib accounted for approximately 23% of the total radioactivity in plasma, based on AUCinf. Metabolites M1 (glucuronidation of M15), M4 (LEQ803, N-demethylation) and M13 (CCI284, N-hydroxylation) were the most abundant metabolites in plasma, representing an estimated 7.78%, 8.60% and 9.39% of total [C]AUC0-48h, and 17.9%, 19.8% and 21.6% of ribociclib AUC0-48h, based on metabolite profiles.

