### 6.1.1 Dosing regimen

LEE011 or LEE011 placebo will be given orally once daily on days 1-21 of each 28 day cycle. Days 22-28 will be a “rest” period from dosing with LEE011 or LEE011 placebo. Tamoxifen, letrozole, and anastrozole will be given orally once daily on a continuous daily schedule (e.g., days 1-28 of each 28 day cycle). Goserelin will be given as an injectable subcutaneous implant on day 1 of every 28 day cycle. There will be no “rest” in the tamoxifen, letrozole, or anastrozole schedule.

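### The crossover ECG schedule does not require any steady-state recording in the post-dose window to which the protocol links QT changes

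*Protocol*

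**What the plan says.** For patients who cross over from placebo, Protocol Section 7.1 requires a baseline recording: "They need to have ECG for QT assessment on the first day before the administration of LEE011". LEE011 may start only if QTcF is below 450 ms. The follow-up instruction gives days but no clock times: "The ECGs should be repeated on cross over Cycle 1 Day 15, on cross over Cycle 2 Day 1 and then as clinically indicated".

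The clock times are in Section 7.2.2.7.1, in a separate table below Table 7-5 introduced as "ECG Schedule of assessments for cross over patients". It sets Cycle 1 Day 1 at pre-dose and both Cycle 1 Day 15 and Cycle 2 Day 1 at *anytime*. Later cycles are as clinically indicated. Table 7-1b marks the same three visits and adds no timing.

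Table 7-5 itself is stricter for originally randomized patients. On Cycle 1 Day 15 it requires triplicate ECGs pre-dose and at 2 h and 4 h post-dose, each post-dose time with a 15-minute window. It requires a 2 h ECG again on Cycle 3 Day 15 and on Cycle 6 Day 1.

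Section 1.2.1.3 explains why timing matters. QT changes become evident by Day 8 and later, once steady state is reached, and "are associated with the maximum drug levels between 1 to 8 h post-dose". Section 6.1.1 makes Days 22-28 of each cycle a rest "period from dosing with LEE011 or LEE011 placebo".

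**The concern.** A crossover patient is as new to LEE011 as a randomized patient was on the first day of the trial, but the timed post-dose ECGs were not carried over. If the one steady-state recording is made just before the daily dose, QTcF is measured near its lowest exposure. Table 6-5 interrupts or reduces LEE011 only on a measured QTcF of at least 481 ms, and its repeat ECGs at 7 and 14 days begin only after such a finding. A patient whose QTcF crosses that threshold only near peak could pass Day 15, stay on full dose, and afterwards have ECGs only as clinically indicated.

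The protocol treats QT as the main crossover risk: Section 6.1 makes tamoxifen patients change to an NSAI and wash out for 35 days because of QT events. Moving to an NSAI does not remove the risk. Section 1.4.1.1 reports QTcF above 480 ms in 11 patients (3.3%) given ribociclib with letrozole. It also reports a sudden death recorded as treatment-related in a patient with grade 3 hypokalemia and a QTcF of 483 ms.

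**Working it through.** **Step 1. Count the ECGs certain to fall 1-8 h post-dose at steady state.**

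| Schedule | ECG | In window at steady state? |
|---|---|---|
| Table 7-5 | Cycle 1 Day 15, 2 h | Yes |
| Table 7-5 | Cycle 1 Day 15, 4 h | Yes |
| Table 7-5 | Cycle 3 Day 15, 2 h | Yes |
| Table 7-5 | Cycle 6 Day 1, 2 h | In the window, but first dose after a rest week; not counted |
| Crossover | Cycle 1 Day 1, pre-dose | No, before any LEE011 |
| Crossover | Cycle 1 Day 15, any time | Steady state, but timing not guaranteed |
| Crossover | Cycle 2 Day 1, any time | No, after the rest week |

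The count is 3 for Table 7-5 and 0 of 3 for crossover. The window is 7 of 24 hours, or 29% of the dosing interval.

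**Step 2. Check the pharmacokinetic model against the protocol's own figures.** Section 1.2.1.5 gives an effective half-life T that "ranged from 12.3 to 42.9 hours across the dose range tested", and a mean accumulation ratio of 1.35 to 3.11. For a mono-exponential model with 24 h dosing, R = 1 / (1 − 2^(−24/T)).

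- T = 12.3 h: R = 1.349
- T = 42.9 h: R = 3.111

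Both stated ratios are reproduced. That range covers all doses tested. For 600 mg alone, Table 1-3 gives geometric mean AUC0-24h without letrozole of 10100 on Day 1 and 24500 on repeat dosing. R = 24500 / 10100 = 2.43, which implies T = 24 × ln 2 / ln(2.43 / 1.43), or about 31 h.

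**Step 3. Trough relative to peak on Cycle 1 Day 15.** With the median Tmax of 2.1 h (Section 1.2.1.5), the decline lasts 24 − 2.1 = 21.9 h and the ratio is 2^(−21.9/T).

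- T = 12.3 h: 0.29
- T = 31 h: 0.61
- T = 42.9 h: 0.70

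**Step 4. What remains on Cycle 2 Day 1.** The last dose is on Day 21 and the visit is on Day 29, so a pre-dose ECG comes 8 × 24 = 192 h after the last dose. The fraction left is 2^(−192/T).

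- T = 12.3 h: 0.002%
- T = 31 h: 1.4%
- T = 42.9 h: 4.5%

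If the ECG follows that day's dose instead, exposure relative to steady state is (1 + R × 2^(−192/T)) / R, which is 74% for T = 12.3 h and 37% for T = 42.9 h.

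**Step 5. Number of patients.** The Amendment 6 summary counts 46 placebo-arm patients on treatment on 03-July-2019. The Amendment 7 summary counts 35 on 08-Jan-2020, of whom 8 had crossed over, leaving 35 − 8 = 27. At the 3.3% rate seen with letrozole, 8 patients imply 0.033 × 8 = 0.3 cases above 480 ms, and all 35 imply 0.033 × 35 = 1.2.

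**The case against.** The case for leaving the schedule alone has real force.

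- *The schedules do not conflict.* A reader might infer that the crossover schedule contradicts Section 1.2.1.3. It does not. An ECG allowed at any time may be taken post-dose, and the section says QT changes are associated with peak levels, not that they arise only then. The schedule is looser than Table 7-5, not incompatible with the rationale.
- *Nothing shows that trough recordings are likely.* It is tempting to argue that patients arrive fasting and dose in clinic, so the ECG will come first. Section 6.1.1.2 fixes fasting before the blood draw and supervised dosing, but not the order of an untimed ECG. Figure 6-1 is not shown in the text available. In-clinic dosing makes a post-dose ECG equally practical.
- *A trough ECG still carries information.* Day 15 is after Day 8, so even a pre-dose recording is at steady state.
- *The high event rates belong elsewhere.* Section 1.2.1.3 reports grade 2 prolongation in 13.5%, and QTcF of 500 ms or more in 5.4%, at 600 mg. Those are single-agent data in advanced solid tumors or lymphomas. Crossover patients take LEE011 with an NSAI, for which 3.3% above 480 ms is the nearer figure.
- *Other safeguards exist.* These are the entry limit of QTcF below 450 ms, electrolytes every two weeks for two cycles, a ban on drugs with known QT risk, and freedom to take unscheduled ECGs.
- *Few patients are affected, and no efficacy inference is involved.* PFS and OS had already been met.

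These points limit the strength and size of the concern. They do not close the gap: none of the safeguards sets the time of the ECG, and a site that records every Day 15 ECG at trough is fully compliant.

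**Conclusion.** The point stands as a cheap improvement to safety monitoring. The crossover schedule guarantees no steady-state ECG in the 1-8 h post-dose window, against three under Table 7-5, and the documents give no reason for the difference. Cycle 1 Day 15 is the only scheduled steady-state ECG. Taken pre-dose, it would see about 29-70% of peak concentration, and about 61% at 600 mg, so it would understate the peak effect without being blind to it. A pre-dose ECG on Cycle 2 Day 1 is essentially off drug, with about 0.002-4.5% remaining.

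The concentration figures assume mono-exponential decline at the effective half-life. The wide range spans all tested doses, and the 600 mg value comes from a ratio of group geometric means with different patient numbers. They describe drug level, and the documents give no formula to convert it into milliseconds of QTcF. The finding is that monitoring can miss a peak prolongation, not that it will.

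**What to change.** In the crossover ECG table of Section 7.2.2.7.1, change the Cycle 1 Day 15 entry from any time to 2 h post-dose with a 15-minute window (4 h would also serve). Table 7-5 already uses both times at that visit. Require the date and time of the LEE011 dose to be recorded with that ECG, as the Table 7-5 footnote does for its pre-dose ECGs. Align the crossover paragraph of Section 7.1 and the ECG row of Table 7-1b with the change.

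No ECG or visit is added. The cost is a wait of about two hours in clinic after the Day 15 dose, and a wording change in three places that must go through a protocol amendment with ethics approval under Section 12.1.
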